- If only the year is specified, then use December 31 of the known year. If an imputed stop date is after last contact date and last contact date is before the data cutoff date, then assign last contact date as the stop date. If an imputed stop date is after last contact date and last contact date is after the data cutoff date, then assign data cut-off date as the stop date.
- If the stop date is completely unknown, then use discharge date or data cut-off date. Discharge date refers to the date of the end of study visit for completed participants or the date of discontinuation for participants that were withdrawn. For any AEs with known start date after the date of discontinuation, the date of last contact will be used as the discharge date. For participants still ongoing in the study at the time of the data cut-off, and for whom no discharge date is available, the date of the data cut-off will be used instead of the discharge date.

Any medication with a start date on the first dosing date and time unknown, will be assumed to be concomitant.

Imputed AE dates will be used for the calculation of duration of AEs as described in [Table 4–1](#).

Table 4–1: Calculation rules for duration of AEs

Data availability	Onset date	Outcome date	Calculation rules
Complete data	D1	D2	$\text{Duration} = D2 - D1 + 1 \text{ d}$
Start date partially or completely missing	--	D2	$\text{Duration} \leq D2 - D0 + 1 \text{ d}$ Notes: D0 is imputed start date per above rules.
End date partially or completely missing	D1	--	For ongoing AE: $\text{Duration} \geq D3 - D1 \text{ d}$ For resolved AE: $\text{Duration} \leq D3 - D1 \text{ d}$ Notes: D3 is imputed end date per above rules.
Start and end date partially or completely missing	--	--	For ongoing AE: $\text{Duration} \geq D3 - D0 \text{ d}$ For resolved AE: $\text{Duration} \leq D3 - D0 \text{ d}$ Notes: D0 is imputed start date and D3 is imputed end date per above rules.

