8.2.3 Adverse events of focus

Rozanolixizumab adverse events of focus (AEOF) include the following categories:

- Headaches
- Aseptic meningitis
- Gastrointestinal disturbances
- Hypersensitivity reactions
- Anaphylactic reactions
- Injection site reaction
- Infections
- Opportunistic infections
- Reductions in albumin and plasma proteins
- Effects on the kidney
- Drug related hepatic disorders
- Effects on lipids

1. The number and percentage of study participants who experience each category of the AEOF will be summarized by most recent dose level prior to onset of the AEOF and RLZ total treatment group. The following summaries will be presented for entire study by SOC, HLT, and PT:

- Treatment-emergent AEOF
- Serious Treatment-emergent AEOF
- Treatment-emergent AEOF by maximum intensity (mild, moderate and severe)

- Treatment-emergent AEOF hypersensitivity reactions, anaphylactic reactions and injection site reactions by ADA
- Severe Treatment-emergent AEOF

2. Incidence of TEAEs will also be summarized by SOC, HLT, PT, and the highest dose level prior to onset of TEAEs and RLZ total for each study cycle, including the number and percentage of study participants and frequency for:

- Treatment-emergent AEOF
- Severe Treatment-emergent AEOF

3. Graphs for AEOF headache in Treatment Period by time of onset (relative to infusion and cycle), severity, causality and duration for each study participant will also be provided. A graph for AEOF headache by participant for participants with at least two headaches in this study will also be provided.

A by-subject listing of all AEOF by category (as listed above) will be provided by treatment group, study cycle and participant. Most recent dose will be presented in listing even when the AE start date is partial. Further details related to the statistical analysis of the above mentioned treatment-emergent AEOFs are provided in [Section 13.7](#).

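### SAP Table 4-1 drops the +1 day when an AE end date is missing, so the upper limit for resolved AEs with a known onset is one day too low

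*SAP*

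**What the plan says.** Table 4-1 in SAP Section 4.2.2 has four rows, according to which AE dates are available. D1 and D2 are the recorded onset and outcome dates; D0 and D3 are the imputed start and stop dates.

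- Complete dates: "Duration} = D2 - D1 + 1 \text{ d".
- Start missing or partial: "Duration} \leq D2 - D0 + 1 \text{ d".
- End missing or partial: "For ongoing AE: $\text{Duration} \geq D3 - D1 \text{ d", and "For resolved AE: $\text{Duration} \leq D3 - D1 \text{ d".
- Both missing or partial: "For ongoing AE: $\text{Duration} \geq D3 - D0 \text{ d", and "For resolved AE: $\text{Duration} \leq D3 - D0 \text{ d".

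The text above the table sends imputed dates into it: "Imputed AE dates will be used for the calculation of duration of AEs as described in" the table. Under the same section, a stop date with only the day missing becomes the last day of that month. With month and day missing it becomes 31 December. Both are cut back to last contact or data cut-off where those apply. A wholly unknown stop date becomes the discharge or cut-off date.

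Section 8.2.3 is where AE duration is visibly displayed: graphs of headache by onset, "severity, causality and duration for each study participant will also be provided".

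**The concern.** The first two rows count days inclusively, so an event that starts and stops on one day lasts 1 day. The last two rows take a plain difference. Imputing the end date does not change how days should be counted, and the SAP gives no reason for switching. As written, the limit shown for an event depends on a different day count according to how completely its end date was recorded.

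For resolved events the switch also matters logically. The table presents D3 - D1 as a ceiling, but under the SAP's own complete-date rule a permitted value lies above it.

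At stake is the accuracy of displayed durations for short events. Headache is the AE whose duration is graphed per participant, and Protocol Section 2.3 names it the most commonly reported adverse drug reaction. Section 4.2.2 also keeps imputed dates out of the listings, so a reader who meets a limit of 0 days could not see the date behind it.

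**Working it through.** **Inputs.** The four rows of Table 4-1 and the imputation rules for start and stop dates, all from SAP Section 4.2.2. The complete-date rule is taken as the definition of true duration.

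**1. The table's own count.** Onset 10 March, stop 31 March, both recorded: 31 - 10 + 1 = 22 days. If the stop day is missing, D3 = 31 March and the end-missing row gives 31 - 10 = 21 days as the maximum.

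**2. When the resolved-event limit fails (known onset).** Let E be the true stop date, with E no later than D3. True duration is E - D1 + 1 and the stated limit is D3 - D1. The limit is broken when E + 1 > D3, which with E ≤ D3 means E = D3. For any earlier stop it holds. With onset and stop in the same month of n days there are n(n + 1)/2 possible onset/stop pairs, and n of them end on the last day:

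| Days in month | Possible pairs | Break D3 - D1 | Break D3 - D1 + 1 |
|---|---|---|---|
| 31 | 31 × 32 / 2 = 496 | 31 | 0 |
| 30 | 30 × 31 / 2 = 465 | 30 | 0 |
| 28 | 28 × 29 / 2 = 406 | 28 | 0 |

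These count date combinations. They are not expected frequencies.

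**3. The zero-day case.** Onset 31 March, stop recorded only as March of that year: D3 = D1, so the table gives at most 31 - 31 = 0 days. The only possible duration is 31 - 31 + 1 = 1 day.

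**4. Ongoing events (known onset).** If the event is still present on D3, its duration is at least D3 - D1 + 1. The stated lower limit D3 - D1 is smaller, so it is true but one day looser than the inclusive count.

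**5. Both dates missing.** Here D0 matters as well as the +1.

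- Start day missing, month not that of first dose: D0 is the first of the month, the earliest possible onset. Take a start recorded as March, true onset 20 March, event ongoing at D3 = 31 March. The true count so far is 31 - 20 + 1 = 12 days. The table says at least 31 - 1 = 30; adding 1 makes it at least 31. The lower limit is false either way.
- Start day missing, month of first dose: D0 is the first-dose date (unless that falls after the recorded end date), which can be later than the true onset. With first dose on 15 March, true onset on 5 March and a resolved event that ended on D3, the true duration exceeds D3 - D0 by (15 - 5) + 1 = 11 days. It exceeds D3 - D0 + 1 by 10 days.

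So the +1 makes the day count consistent in this row but cannot make either inequality a valid limit.

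**6. Relative size.** One day is 100% of a 1-day event, 50% of 2 days, 33.3% of 3, 14.3% of 7 and 3.3% of 30.

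**The case against.** The best defence is that the last two rows state inequalities, not durations, and that with a known onset most of them remain true. This stands in part and limits the point in three ways.

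- A reader might infer that every AE with a partial end date is reported one day short. The documents do not support that: the resolved-event limit fails only when the true stop is D3, and the ongoing limit with a known onset is never false.
- A reader might infer that same-day events are generally shown as lasting 0 days. They are not. A same-day event on 10 March with the stop recorded as March gives at most 21 days, which is true. The zero arises only when D3 falls on the onset date (or on D0).
- A reader might infer that adding 1 day throughout would repair the whole table. Step 5 shows that it does not for the both-missing row. The start-missing row has the same weakness, because it relies on the same D0.

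A second defence is that a plain difference could be a deliberate convention for ends that were not observed. The rest of the SAP speaks against it. Section 9.11 adds 1 when the interval ends in censoring. Section 11.4 adds 1 to hospital days while imputing missing discharge dates. Section 8.1 adds 1 to time in study. The relative-day label after the last infusion (Section 3.2.1.1) has no +1, but it is a position in time, not a duration.

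The third defence, that little depends on this, is fair. TEAE status in Section 8.2.1 rests on onset or worsening relative to dosing and the 56-day window, not on duration, and all analyses are descriptive. That headache is common says nothing about how often its end date is incomplete; the documents give no figure.

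**Conclusion.** The inconsistency is real and minor. For resolved AEs with a known onset, the stated upper limit is one day too low: it is false when the true stop equals D3, and it reads as at most 0 days when D3 is the onset date. For ongoing AEs with a known onset, the limit is correct but one day loose. In the both-missing row the day count is inconsistent in the same way, and the inequalities are unreliable for a separate reason, the choice of D0.

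The size is one day per affected event, proportionally largest for the shortest events. It reaches only displays of AE duration, notably the headache graphs. It does not touch TEAE classification or the primary safety counts. The conclusion assumes that the complete-date row is the intended definition, that a resolved event ended no later than D3, and that an ongoing event was still present on D3. How many AEs are affected cannot be estimated from the documents.

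**What to change.** In Table 4-1:

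- End-missing row: replace D3 - D1 with D3 - D1 + 1, for resolved (≤) and ongoing (≥) events.
- Both-missing row: use D3 - D0 + 1 so that days are counted the same way throughout, drop the claim that it is a limit, and label it an approximate imputed duration. A footnote should say that D0 may be the earliest possible onset or later than it.

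The cost is one table edit and a small programming change, with no new data and no effect on study conduct. Section 4.4 has the Submission Cut (data to 08 July 2022) run all SAP analyses, so final headache graphs could differ by one day from those already produced for events with incomplete end dates. A sentence in the amendment table would explain this.

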4.2.3 Impact of the coronavirus disease 2019 (COVID-19) on study data

Missing data is expected to be one of the major implications of the COVID-19 pandemic. The following approaches/strategies will be applied to assess the impact of COVID-19 in this study.

- Added an electronic Case Report Form (eCRF) page “COVID-19 Impact”, including impacted visits, impact categories and relationship to COVID-19;
- Additional fields were added in protocol deviation specification documents to record protocol deviations relationship to COVID-19;
- Included additional summary analyses based on the timing of COVID-19 impact [during/post COVID-19 pandemic based on COVID-19 start date 20-Mar-2020 and COVID-19 end date 05-May-2023 (WHO, 2023)].

4.3 Handling of repeated and unscheduled measurements

All repeated and unscheduled measurements will be presented in the listings, where applicable. The following general rules will apply to all repeated and unscheduled measurements:

- For repeated or unscheduled measurements obtained prior to the first dose of IMP the latest non-missing value (scheduled or unscheduled) will be used in the calculation of descriptive statistics (ie Screening);
- For repeated or unscheduled measurements obtained at any time point after the first dose of IMP, the scheduled values (if non-missing) will always be used in the calculation of changes from Baseline and for the descriptive statistics (ie, in summaries by time point). If repeated scheduled values are obtained at any time point, the latest non-missing values will be used.

See [Section 8.4.2](#) for the rules applied to ECG triplicate measurements.

4.4 Interim analyses and data monitoring

Submission Cut and Day 120 cut will be conducted during the study. For Submission Cut, all the analyses specified in the SAP will be performed using all the data of all participants till 08 July 2022 for submission purposes. For Day 120 cut, only selected analyses of safety in the SAP will be performed using all the data till 07 October 2022.

An overarching Rozanolixizumab program IDMC (pIDMC) will oversee the safety of this study by reviewing safety data at periodic timepoints with other Rozanolixizumab studies. The scope and role of the overarching pIDMC will be described in overarching IDMC charter and its study specific attachment.

Data requirements for each interim cut are summarized below:

- Submission Cut: PK, NAb, and ADA are required. PK and ADA data will be transferred to PXL 7 weeks after the MG0003 database lock. Bioanalysis of PK and ADA samples takes around 10 weeks. In order to meet the timelines for the PK/ADA data transfer to PXL, PK and ADA samples will need to be sent to the LGC lab around 10 weeks before the data transfer.
- Day 120 cut: PK, NAb, and ADA are required. Available samples transferred to Lab around 10 weeks before data transfer, data transfer around 1.5 weeks before the review.

4.5 Multicenter studies

Individual center results will not be displayed.

4.6 Multiple comparisons/multiplicity

Adjustment for multiplicity will not be required since all analyses will be descriptive in nature.

4.7 Use of an efficacy subset of subjects

All efficacy data will be summarized only, and there is no sensitivity analysis planned.

4.8 Active-control studies intended to show equivalence

Not applicable.

4.9 Examination of subgroups

4.9.1 General subgroups

The continuous secondary efficacy endpoints will be evaluated for subgroups of interest including:

- Age (18-<65, \geq 65 years)
- Age (18-<65, 65-<85, \geq 85 years)
- Sex (male, female)
- Region (North America, Europe, and Asia [excluding Japan], Japan)
- Stratification factor in MG0003 - MG-specific autoantibody (muscle-specific kinase [MuSK] $^{+/-}$ or acetylcholine receptor [AChR] $^{+/-}$)

Notes: Region as specified for MG0003 will be used. The stratification factors MuSK($^{+/-}$) and AChR($^{+/-}$) will be based on the derived values from MG0003 subgroup analysis.

The MG-ADL scores and change from Baseline will be summarized in the five subgroups as above and additional subgroups as follow:

- Duration of disease at MG0003 Baseline (<median, \geq median)
- MGFA disease class at MG0003 Baseline
- Thymectomy at MG0003 Baseline (yes, no)
- MG0007 Baseline MG-ADL category (<5, \geq 5).

These evaluations will be descriptive; no statistical testing of treatment-by-subgroup interactions nor statistical testing of treatment effects within subgroups will be carried out.

Subgroup analyses will only be performed for cases where there are at least 5 study participants in a specific category.

4.9.2 Examination of weight subgroups and administered doses

To support the goal of a fixed dosing strategy for Rozanolixizumab, additional subgroup analyses will be performed by administered dose group for each weight subgroup below:

- Weight (< 50kg, 50 - <70 kg, 70 - <100kg, \geq 100kg, total)
- Administered dose (RLZ 280mg, RLZ 420mg, RLZ 560mg, RLZ 840mg, RLZ 1120mg, RLZ Total)

4.9.3 Manual push analysis

Additionally, participants who have used manual push will be flagged in all listings. Separate listings for treatment-emergent adverse events and total IgG will be provided.

5 STUDY POPULATION CHARACTERISTICS

For analysis using FAS and ES, the first cycle treatment group includes ‘Not Treated’ group.

5.1 Subject disposition

The following outputs will be created.

Summaries:

- **Reasons for screen failures** (as collected on the Study Termination Screen Failure CRF page) will be tabulated using the ES for overall. Additionally, the reasons for screen failures will be summarized by during and post- the COVID-19 pandemic based on the screen failure date relative to the pandemic cut-off date.
- **Disposition of study participants screened** will be tabulated using the ES for overall, by region and by site. In this summary, the site number, principal investigator name, first participant in date and last participant out date, will be captured by first actual treatment and by each analysis set (FAS and SS).
- **Disposition of analysis sets** will be summarized by the first cycle treatment group, RLZ total, total and analysis sets (ES, FAS and SS) using the ES.
- **Disposition and discontinuation reasons** will be tabulated using the FAS and SS, and will contain the number and percentage of study participants by treatment group, overall and by during and post- the COVID-19 pandemic who:
 - Started Study
 - Completed Study
 - Discontinued Study with primary reason for discontinuation (primary reason for premature study termination as collected in the Study Termination Enrolled CRF)

Note: The summary by during and post- the COVID-19 pandemic will be based on the start, completed and discontinuation date relative to the pandemic cut-off date which will be presented in the same table. The discontinuation reason in each period will also be summarized. Discontinuation due to COVID-19 pandemic as well as discontinuation due to transition to MG0020 study will be summarized as sub-category under “Other” reason.

- **Discontinuation due to AEs** will be presented using the FAS and SS to display the total number of study participants who discontinued the study due to AEs by treatment group, RLZ total, total and the categories: AE serious fatal, AE non-fatal and other (AE non-serious fatal).
- **Count of participant by visit** using SS will summarize the number of participants at each visit by treatment group.

- **Impact of COVID-19** will be presented using the FAS to display the number and percentage of participants in each impact category by treatment group, RLZ total, total and visit.

Listings of study participant disposition using ES, study discontinuation using FAS, study participants who did not meet study eligibility criteria using ES, and participant analysis sets using ES will be provided.

5.2 Important protocol deviations

A summary of number and percentage of study participants with an important protocol deviation by relationship to COVID-19, first actual treatment group, RLZ total and total will be provided for the FAS. Additionally, the summary will be repeated by during and post- the COVID-19 pandemic based on the deviations start date relative to the pandemic cut-off date.

A listing of important protocol deviations will be provided based on the FAS.

6 DEMOGRAPHICS AND OTHER BASELINE CHARACTERISTICS

For analysis using FAS and ES, the first cycle treatment group includes 'Not Treated' group.

6.1 Demographics

Demographic variables will be summarized on the FAS and SS, by categories mentioned below using descriptive statistics by first actual treatment group, RLZ total and total. Additional subgroup summary will be presented by during and post- the COVID-19 pandemic based on the enrolled date relative to the pandemic cut-off date using FAS.

Categories for continuous variables (including n, mean, SD, Median, Min and Max):

- Age at the time of study MG0003 entry (years)
Notes: Missing age will be calculated as year of informed consent signed – year of birth
- Height (cm)
- Weight (kg)
- Body mass index (BMI, kg/m²), to be calculated as: BMI = Weight (kg) / (Height (m))²

Categorical variables (using frequency counts and percentages):

- Age (18-<65, 65-<85, ≥85 years)
- Age (≤18, 19-<65, ≥65 years)
- BMI (<30 kg/m², ≥30 kg/m²)
- Weight (<50kg, 50kg-<70 kg, 70-<100kg, ≥100kg)
- Weight (<50kg, ≥50kg)
- Weight (<70kg, ≥70kg)
- Sex (Male, Female)

- Race (American Indian or Alaskan native, Asian, Black, Native Hawaiian or Other Pacific Islander, White, Other/Mixed)
- Ethnicity (Hispanic or Latino, Not Hispanic or Latino)
- Region (North America, Europe, Asia [excluding Japan], Japan)
- Country
- Study where the study participant comes from: MG0003 or MG0004
- Worsening of disease (yes, no)
- Needed additional therapies in the observation period of MG0003 and entered MG0007 (yes, no)

Note: Worsening of disease is defined as the worsening of gMG symptoms (eg, an increase of 2 points on the MG-ADL or 3 points on the QMG scale) between two consecutive visits based on the Investigator's discretion.

A by-participant listings of demographics will be provided using the FAS. Childbearing potential and lifestyle will be listed using the ES separately.

6.2 Baseline characteristics

The following variables will be summarized by treatment group and RLZ total for the SS. The baseline values are derived according to [Section 3.3](#).

- MG0003 Baseline MuSK antibody status (positive, negative)
- MG0003 Baseline AChR antibody status (positive, negative)
- MG0007 Baseline MuSK antibody status (positive, negative)
- MG0007 Baseline AChR antibody status (positive, negative)
- Baseline MG-ADL score
- Baseline MG-ADL category (<5 , ≥ 5)
- Baseline QMG score
- Baseline MG-C score
- Baseline total IgG value
- Age at initial MG diagnosis
- Duration of disease at MG0003 Baseline ($<\text{median}$, $\geq \text{median}$)
- MGFA disease class at MG0003 Baseline
- Thymectomy at MG0003 Baseline (yes, no)

Note: Duration of disease at MG0003 Baseline = (Date of Randomization in MG0003-Date of Initial MG Diagnosis+1)/365.25; MG0003 MuSK and AChR antibody status are based on the derived values from MG0003 model analysis.

6.3 Medical history and concomitant diseases

Any medical conditions that were not reported in MG0003/MG0004 will be captured on CRF of this study and listed using the FAS.

6.4 Prior and concomitant medications

The number and percentage of participants taking Prior or Concomitant medications will be summarized using the SS by Anatomical Therapeutic Chemical (ATC) class, presenting as Anatomical Main Group (ATC Level 1), Pharmacological Subgroup (ATC level 3), Preferred Term (PT), actual treatment group, and RLZ total for entire study.

Additionally, rescue medications are those that are mentioned in Protocol section 6.5.3 and identified:

- if Rescue Medication is ticked as yes on CRF Concomitant Medication page
- Or PEX as procedure entered on CRF Concomitant Medical Procedure page

The start date of rescue medication should be on or after Baseline. All rescue medications will be summarized using the SS.

Medications classified as Prior or Concomitant will be listed using the FAS. A by-participant listing of concomitant procedures will also be listed using the FAS. Originally reported dates will be used for listings.

